# 7.5.1 Long Term Follow-Up

Survival status and subsequent therapies will be collected during long term follow-up (LTFU) every 6 months (+/- 4 weeks), by phone or chart review, for 3 years or until study closure. Additionally, the following data will be collected: date of death, date of radiographic and/or PSA progression, start and stop dates for subsequent therapies.

# 7.6 Agent Administration

Treatment will be administered on an outpatient basis. Expected adverse events and potential risks are described in **Section 7.9.** Appropriate delays and modifications are described in **Section 8.1** and **Section 8.2**, respectively. Events that result in dose adjustments for each drug (i.e. increases, decreases, delaying, or omitting therapy) related to the AE after therapy has been initiated or AEs because of other therapies, such as surgery and radiation therapy, are considered treatment-limiting adverse events. Treatment-limiting adverse events for ascorbic acid and olaparib are described in **Section 8.1**. No investigational or commercial agents or therapies older than those described below may be administered with the intent to treat the subject's malignancy. The drug regimen for this trial is shown below in **Table 2**.

**Table 2: Regimen Description** 

Regimen Description				
Agent	Dose	Route	Schedule	Cycle Length
Olaparib 	300 mg	Oral	Twice daily, days 1-28	28 days (4 weeks)
Ascorbic Acid	1 g/kg 	0.75-1 gram per minute IV 	Twice weekly  First dose on day 1 of the cycle	

- 1. Olaparib: two 150 mg tablets orally, with or without food, twice daily. The tablets are to be swallowed whole (do not chew, dissolve, or open the tablets). Administration should be in accordance with the package insert. $^{34}$
- 2. For a subject weighing 75 kg, the goal dose is 75 grams (1 g/kg), and the titrated dose schedule is  $18.75 \, \text{g}$ ,  $37.5 \, \text{g}$ , and  $56.25 \, \text{g}$  for cycle 1 only. Rounding the calculated doses to 19 g, 38 g, and  $56 \, \text{g}$  is acceptable. Subsequent doses would be 75 g. The maximum allowed dose for patients weighing over  $100 \, \text{kg}$  is  $100 \, \text{g}$ .
- 3. Infusion time is approximate (± 15 minutes) and may need to be adjusted based on patient tolerability. Infusion time is estimated to be between 90-120 minutes.
- 4. The ideal schedule for ascorbic acid is 3-4 days apart for administration. However, ascorbic acid can be safely administered on consecutive days (at least 24 hours apart). The day that ascorbic acid can be administered can be shifted in the event of holidays, inclement weather, and other reasons for clinic closure to even three consecutive days.

Subsequent ascorbic acid infusions may not be given less than 24 hours apart.

Acute reactions will be managed using standard therapy for acute drug reactions as per institutional standard of care.

# 7.6.1 Olaparib Administration

Patients will be administered olaparib twice daily at 300mg continually. Two 150mg olaparib tablets should be taken twice daily at the same time each day, approximately 12 hours apart with one glass of water. The olaparib tablets should be swallowed whole and not chewed, crushed, dissolved, or divided. Olaparib tablets can be taken with or without food.

# 7.6.2 Ascorbic Acid Administration

For the first cycle, on cycle 1 day 8, collect blood for CTCs and then start Ascorbic Acid. The first three doses of ascorbic acid will be titrated as such: 0.25~g/kg, 0.5~g/kg, 0.75~g/kg in 1000ml of sterile water (not to exceed 500 mL per hour). If tolerated, the subsequent doses will be 1 g/kg. Infusions will be twice a week, and should not be less than 24 hours apart. It is recommended that ascorbic acid be given through a port due to frequency of infusion, but a port is not required.

# 7.7 Concomitant, Supportive, and Restricted Medication and Supportive Care Guidelines

The use of any natural/herbal products other than traditional remedies should be discouraged, but use of these products, as well as any medication or vaccine including overthe-counter or prescription medicines, vitamins, and/or herbal supplements that the patient is receiving at the time of enrolment or receives during the study must be recorded in the case report form (CRF), along with reason for use, dates of administration including start and end dates, and dosage information including dose and frequency. Supportive care, including but not limited to anti-emetic medications, may be administered at the discretion of the Principal Investigator or Co-Investigators. Concurrent treatment with bisphosphonates is allowed. All concomitant treatments, including blood and blood products, must be reported on the case report form (CRF).

In order to better differentiate adverse events related to investigational study agents from those related to the COVID-19 vaccine, it is recommended where possible, that subjects not receive any dose of the COVID-19 vaccine within 3 days of study drug. If a live COVID-19 vaccine becomes available to the public, an exemption specifically for live COVID-19 vaccines will be discussed with the Protocol Manager.

#### **Restricted concomitant medications**

Medications prohibited 6 months prior to enrollment

5-alpha reductase inhibitors are allowed if subject has been taking stable dose of medication for prior 6 months.

Strong or moderate CYP3A inhibitors

Known strong CYP3A inhibitors (e.g. itraconazole, telithromycin, clarithromycin, boosted protease inhibitors, indinavir, saquinavir, nelfinavir, boceprevir, telaprevir) or moderate CYP3A inhibitors (ciprofloxacin, erythromycin, diltiazem, fluconazole, verapamil) should not be taken with olaparib. See this link for a complete list of known CYP3A inhibitors: https://www.fda.gov/drugs/drug-interactions-labeling/drug-development-and-drug-interactions-table-substrates-inhibitors-and-inducers. During the study, if co-administration or a strong or moderate inhibitor is required because there is no suitable alternative medication, dose of olaparib should be reduced for the period of concomitant administration.

- Strong CYP3A inhibitors reduce the dose of olaparib to 100 mg twice daily for the duration of concomitant therapy with the strong inhibitor and for 5 half-lives afterwards.
- Moderate CYP3A inhibitors reduce the dose of olaparib to 150 mg twice daily for the duration of concomitant therapy with the moderate inhibitor and for 3 half-lives afterwards.
- After the washout of the inhibitor is complete, the olaparib dose can be re-escalated.

Strong or moderate CYP3A inducers

Strong (e.g. phenobarbital, phenytoin, rifampicin, rifabutin, rifapentine, carbamazepine, nevirapine, enzalutamide and St. John's Wort) and moderate (e.g. bosentan, efavirenz, modafinil) CYP3A inducers should not be taken with olaparib. See this link for a complete list of known CYP3A inhibitors: https://www.fda.gov/drugs/drug-interactions-labeling/drug-development-and-drug-interactions-table-substrates-inhibitors-and-inducers.

Effect of olaparib on other drugs

Based on limited in vitro data, olaparib may increase the exposure to substrates of CYP3A4, BCRP, OATP1B1, OCT1, OCT2, OAT3, MATE1 and MATE2K.

Based on limited in vitro data, olaparib may reduce the exposure to substrates of 2B6 (and potentially substrates of CYP2C9, CYP2C19 and P-gp).

Caution should be observed if statins or sensitive CYP3A4 substrates are co-administered.

Appropriate clinical monitoring is recommended for patients receiving P-gp substrates or CYP3A substrates with a narrow therapeutic margin concomitantly with olaparib.

# Examples of substrates include:

- CYP3A4 substrates with narrow therapeutic margin: e.g. cisapride, cyclosporine, ergot alkaloids, fentanyl, pimozide, sirolimus, tacrolimus and warfarin.
- Sensitive CYP3A4 substrates: e.g. buspirone, felodipine, fluticasone, lovastatin, quetiapine, saquinavir, sildenafil and simvastatin.
- CYP2B6 substrates: e.g. bupropion and efavirenz.
- OATP1B1 substrates: e.g. bosentan, glibenclamide, repaglinide, statins and valsartan.
- OCT1, MATE1 and MATE2K substrates: e.g. metformin.
- OCT2 substrates: e.g. cimetidine and metformin.
- OAT3 substrates: e.g. furosemide and methotrexate.
- BCRP substrates: e.g. methotrexate and rosuvastatin.
- P-gp substrates: e.g. simvastatin, pravastatin, dabigatran, digoxin and colchicine.

# Anticoagulant Therapy

Patients who are taking warfarin may not participate in this trial due to potential warfarin resistance due to its interaction with ascorbic acid. Non-vitamin K antagonist oral anticoagulants (NOACs), subcutaneous heparin and low molecular weight heparin may be given concomitantly with olaparib and INR monitoring is not required. If NOACs are used, it is preferable to avoid CYP3A substrates (e.g. apixaban and rivaroxaban) if possible.

# Anti-emetics/Anti-diarrheals

If a patient develops nausea, vomiting, and/or diarrhea, then these symptoms should be reported as AEs (see **Section 9.5**) and appropriate treatment of the event given.

# Administration of other anti-cancer agents

Patients must not receive any other concurrent anti-cancer therapy, including investigational agents, while on study treatment. No other anti-cancer therapy (chemotherapy, immunotherapy, hormonal therapy (Hormone replacement therapy [HRT] is acceptable), radiotherapy, biological therapy or other novel agent) is to be permitted while the patient is receiving study medication.

# Vaccines

Live virus and live bacterial vaccines should not be administered whilst the patient is receiving study medication and during the 30 day follow up period. An increased risk of infection by the administration of live virus and bacterial vaccines has been observed with conventional chemotherapy drugs and the effects with olaparib are unknown.

# Other prohibited products

It is prohibited to consume grapefruit juice while on olaparib therapy. Patients must not consume grapefruit or Seville oranges while on treatment with olaparib.

See **Table 3** for summary of Prohibited Medications.

**Table 3: Prohibited medications** 

Prohibited medication/class of drug:				
Anticancer therapy: Chemotherapy Immunotherapy Hormonal therapy Radiotherapy (except palliative) Biological therapy Other novel agents	Not permitted while the patient is receiving study medication			
Live virus vaccines Live bacterial vaccines	Not permitted while the patient is receiving study medication and during the 30 day follow up period. An increased risk of infection by the administration of live virus and bacterial vaccines has been observed with conventional chemotherapy drugs and the effects with olaparib are unknown.			

# 7.8 Contraception

Male patients must use a condom during treatment and for 3 months after the last dose of olaparib when having sexual intercourse with a pregnant woman or with a woman of childbearing potential. Female partners of male patients should also use a highly effective form of contraception (as described in **Appendix C**) if they are of childbearing potential. Male patients should not donate sperm throughout the period of taking olaparib and for 3 months following the last dose of olaparib.

For details of acceptable methods of contraception refer to **Appendix C** Acceptable Birth Control Methods.

# 7.9 Expected Adverse Events

# 7.9.1 Ascorbic Acid

Too rapid intravenous administration of the solution may cause temporary faintness or dizziness.

The most common side effects of ascorbic acid include: pain and swelling at administration sites, nausea, vomiting, diarrhea, dry mouth, loss of appetite, muscle weakness, dizziness, headache, phlebitis, hypertension, fatigue, and leakage of protein.

Less common side effects of ascorbic acid include: acute and chronic nephropathy, kidney stones, renal failure, hypernatremia, hypoalbuminemia, hyperglycemia, and hypokalemia.

Of note, it has been reported that patients with a history of glucose-6-phosphate dehydrogenase deficiency experienced hemolysis.

# 7.9.2 Olaparib

The most common side effects of olaparib include: nausea, fatigue (including asthenia), anemia, vomiting, diarrhea, decreased appetite, headache, neutropenia, dysgeusia, cough, dyspnea, dizziness, dyspepsia, leukopenia, thrombocytopenia, and upper abdominal pain.

Less common side effects of olaparib include: constipation, lymphopenia, mean corpuscular volume [MCV] elevation, blood creatinine increased, hypersensitivity, dermatitis, stomatitis, MDS/AML, and rash.

In a small number of patients, pneumonitis, and new primary malignancies have been reported, however totality of data from the whole development program does not support a conclusion that there is a causal relationship between olaparib and these events.

#### 7.10 Overdose

An overdose is defined as the accidental or intentional administration of any dose of a product that is considered both excessive and medically important. All occurrences of overdose must be reported as SAEs (see **Section 9.5.1**).

There is currently no specific treatment in the event of overdose with olaparib and possible symptoms of overdose are not established.

Olaparib must only be used in accordance with the dosing recommendations in this protocol. Any dose or frequency of dosing that exceeds the dosing regimen specified in this protocol should be reported as an overdose. The Maximum Tolerated Dose is 300 mg bid (tablet).

Overdose with ascorbic acid may cause nausea, vomiting, diarrhea, facial flushing, rash, headache, fatigue or disturbed sleep. If overdose of ascorbic acid occurs, immediately discontinue administration, avoiding additional intake of ascorbic acid until symptoms are managed appropriately.

Ascorbic acid must only be used in accordance with the dosing recommendations in this protocol. Any dose or frequency of dosing that exceeds the dosing regimen specified in this protocol should be reported as an overdose. The Maximum Tolerated Dose is  $1\,\mathrm{g/kg}$ , with the maximum dose of  $100\,\mathrm{g}$  for patients weighing over  $100\,\mathrm{kg}$ .

Adverse reactions associated with overdose should be treated symptomatically and should be managed appropriately.

If an overdose on an AstraZeneca or McGuff study drug occurs in the course of the study, then investigators or other site personnel inform appropriate AstraZeneca or McGuff

representatives **within one day** i.e. immediately, but no later than **the end of the next business day** of when he or she becomes aware of it.

The designated AstraZeneca or McGuff representative works with the investigator to ensure that all relevant information is provided to AstraZeneca or McGuff Patient Safety data entry site.

# 8.0 DOSING DELAYS/MODIFICATIONS

# 8.1 Dosing Delays

All scheduled cycles occur over a 28-day period. If necessary, treatment may be delayed for up to 4 weeks. If treatment is delayed more than two weeks, the Principal Investigator must be contacted for further instructions on continued treatment. Additional delays or modifications to the treatment schedule must be approved by the Protocol Chair. When the delay is due to toxicity, then the next cycle may begin with a dose reduction.

Ascorbic acid will be withheld for the following drug-related toxicities:

- $Cr \ge 1.6 \times ULN$  (for patients with  $Cr \ge 1.6 \times ULN$ , calculated or measured creatinine clearance must be  $\ge 50 \text{ mL/minute}$  (Cockcroft-Gault))
- Common Terminology Criteria for Adverse Events (CTCAE) Grade 3 or 4 non-hematologic toxicity excluding asymptomatic electrolyte aberrations
- Any AE, laboratory abnormality, or intercurrent illness that, in the judgement of the investigator, warrants delaying the dose of study medication

Olaparib will be withheld for the following drug-related toxicities:

Absolute neutrophil count
 Platelets
 Hemoglobin
 Total bilirubin
 AST (SGOT)/ALT(SGPT)
 ≤ 750/ mm³, see Table 8
 ≤ 8 hgb, If < 10, see Table 7

 ≥ 1.5XULN
 ≥ 2.5 x ULN (<5x ULN if with known liver m

• AST (SGOT)/ALT(SGPT)  $\geq 2.5 \text{ x ULN (<}5\text{x ULN if with known liver metastases}$  provided bilirubin is normal)

- Common Terminology Criteria for Adverse Events (CTCAE) Grade 3 or 4 non-hematologic toxicity excluding asymptomatic electrolyte aberrations
- Any AE, laboratory abnormality, or intercurrent illness that, in the judgement of the investigator, warrants delaying the dose of study medication

If dosing parameters for Ascorbic Acid are not met, study participants may continue with olaparib therapy. If dosing parameters for olaparib or are not met, study participants may continue with Ascorbic Acid therapy. Dose interruptions are allowed as required, for a maximum of 4 weeks. Patients who require an interruption in olaparib or ascorbic acid for >4 weeks due to toxicity must permanently discontinue study drug unless an exemption is granted by the protocol chair (Refer to section 13.6 for stopping rule). Where toxicity reoccurs following re-challenge with study treatment, then the patient should be considered for dose reduction or must permanently discontinue study treatment per investigator judgement.

#### 8.2 Dose Modifications

Patients enrolled in this study will be evaluated clinically and with standard laboratory tests before and at regular intervals during their participation in this study as specified in **Section 7.3.1.** The NCI CTCAE v.5.0 will be used to grade adverse events.

At each study visit for the duration of their participation in the study, patients will be evaluated for adverse events (all grades), serious adverse events (SAEs), and adverse events that require study drug interruption or discontinuation.

Adverse events possibly related to either study drug must be resolved to grade 1 or baseline prior to resumption of dosing.

Patients who experience grade 3 of 4 toxicities (individually defined in **Section 8.1**) that are eligible for retreatment will be dose reduced. After a two-week dose delay, if the grade 3 or 4 toxicity resolves to grades 0-2 (grade 2 peripheral neuropathy must resolve to grade 1 if interfering with instrumental ADL), then the following dose reductions are to be applied.

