- [11] Concomitant use of known strong CYP3A inhibitors (eg. itraconazole, telithromycin, clarithromycin, protease inhibitors boosted with ritonavir or cobicistat, indinavir, saquinavir, nelfinavir, boceprevir, telaprevir) or moderate CYP3A inhibitors (eg. ciprofloxacin, erythromycin, diltiazem, fluconazole, verapamil). The required washout period prior to starting study treatment is 2 weeks. See the following link for a complete list of known CYP3A inhibitors:

https://www.fda.gov/drugs/drug-interactions-labeling/drug-development-and-drug-interactions-table-substrates-inhibitors-and-inducers

[12] Concomitant use of known strong (eg. phenobarbital, enzalutamide, phenytoin, rifampicin, rifabutin, rifapentine, carbamazepine, nevirapine and St John's Wort ) or moderate CYP3A inducers (eg. bosentan, efavirenz, modafinil). The required washout period prior to starting study treatment is 5 weeks for enzalutamide or phenobarbital and 3 weeks for other agents. See the following link for a complete list of known CYP3A inhibitors:

https://www.fda.gov/drugs/drug-interactions-labeling/drug-development-and-drug-interactions-table-substrates-inhibitors-and-inducers

- [13] Have moderate or severe cardiovascular disease:
  - Has the presence of cardiac disease, including a myocardial infarction within six months prior to study entry, unstable angina pectoris, New York Heart Association Class III/IV congestive heart failure, or uncontrolled hypertension.
  - Resting ECG indicating uncontrolled, potentially reversible cardiac conditions, as judged by the investigator (eg., unstable ischemia, uncontrolled symptomatic arrhythmia, congestive heart failure, QTc prolongation >500 ms, electrolyte disturbances, etc.), or patients with congenital long QT syndrome.
- [14] Have uncontrolled intercurrent illness, including but not limited to ongoing or active infection, symptomatic congestive heart failure, unstable angina pectoris, cardiac arrhythmia, or psychiatric illness/social situations that would limit compliance with study requirements.
- [15] Have other malignancy unless curatively treated with no evidence of disease for ≥5 years except adequately treated non-melanoma skin cancer.
- [16] Have persistent toxicities (>Common Terminology Criteria for Adverse Event (CTCAE v5.0) grade 2) caused by previous cancer therapy, excluding alopecia.
- [17] Patients with myelodysplastic syndrome/acute myeloid leukemia or with features suggestive of MDS/AML.

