# 7.4 Duration of Therapy and Criteria for Removal from Study

Patients will be removed from study when any of the criteria listed apply. The reason for study removal and the date the patient was removed must be documented in the Case Report Form.

In the absence of treatment delays due to adverse event(s), treatment may continue until one of the following criteria applies:

- Disease progression by RECIST criteria v1.1 (Appendix E) or bone progression per PCWG3 (see Section 7.4.1)
- Disease progression by symptomatic assessment
- PSA doubling from baseline value, confirmed by a second value at least 4 weeks apart, with a minimum time since initiation of therapy of 12 weeks (see **Section 7.4.1**)
- Intercurrent illness that prevents further administration of treatment
- Unacceptable adverse event(s): toxicity (defined in **Section 8.1**) that has not recovered in 2 weeks or if the same toxicity recurs at the decreased dose (unless there is strong evidence of clinical benefit to justify continuation of dosing with study treatment, and the rationale must be discussed with the Principal Investigator before a decision is made)
- The subject or legal representative (such as a parent or legal guardian) withdraws consent for treatment
- If, in the opinion of the Investigator, a change or temporal or permanent discontinuation of therapy would be in the best interest of the subject
- Patient is noncompliant with respect to taking drugs, keeping appointments, or having tests required
- for the evaluation of drug safety and efficacy Bone marrow findings consistent with myelodysplastic syndrome (MDS)/acute myeloid leukemia (AML)
- Potential Hy's Law cases (AST or ALT ≥3x ULN and TBL ≥2x ULN with no other reason)

Because an excessive rate of withdrawals can render the study uninterpretable, unnecessary withdrawal of patients should be avoided. When a patient discontinues

treatment early, the investigator should make every effort to contact the patient and to perform a final evaluation. The reasons for withdrawal should be recorded.

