#### 8.2.1 Ascorbic Acid Dose Modification

One dose modification of ascorbic acid is allowed to 0.75 g/kg (if two dose reductions are required, the patient will go off protocol treatment).

Ascorbic acid dose modifications for symptoms other than grade 3 or 4 toxicities should be discussed with and approved by the Protocol Chair.

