# Management of anemia

Table 7 Management of anemia

Hemoglobin	Action to be taken	
Hb < 10 but ≥ 8 g/dl (CTCAE Grade 2)	Give appropriate supportive treatment and investigate causality. Investigator judgement to continue olaparib with supportive treatment (eg transfusion) $or$ interrupt dose for a maximum of 2 weeks. If repeat Hb < 10 $but \ge 8$ g/dl, dose interrupt (for max of 2 weeks) until Hb $\ge 10$ g/dl and upon recovery dose reduction to 250 mg twice daily as a first step and to 200 mg twice daily as a second step may be considered.	
Hb < 8 g/dl (CTCAE Grade 3)	Give appropriate supportive treatment (e.g. transfusion) and investigate causality.  Interrupt olaparib for a maximum of 2 weeks until improved to Hb ≥ 10 g/dl.  Upon recovery dose reduce to dose should be reduced to 200 mg twice daily as first step. If the reduced dose of 200 mg twice daily is not tolerable, no further dose reduction is allowed and study treatment must be discontinued.	

Common treatable causes of anemia (e.g. iron, vitamin B12, or folate deficiencies and hypothyroidism) should be investigated and appropriately managed. In some cases management of anemia may require blood transfusions.

Management of neutropenia, leukopenia and thrombocytopenia

Table 8 Management of neutropenia, leukopenia and thrombocytopenia

Toxicity	Study treatment dose adjustment
CTCAE Grade 1-2	Investigator judgement to continue treatment or if dose interruption, this should be for a maximum of 2 weeks; appropriate supportive treatment and causality investigation
CTCAE Grade 3-4	Dose interruption until recovered to CTCAE grade 1 or better for a maximum of 2 weeks. If repeat CTCAE grade 3-4 occurrence, dose reduce olaparib to 250 mg twice daily as a first step and 200 mg twice daily as a second step
	Discontinue therapy in cases of febrile neutropenia and thrombocytopenia associated with hemorrhage

Adverse event of neutropenia and leukopenia should be managed as deemed appropriate by the investigator with close follow up and interruption of study drug if CTCAE grade 3 or worse neutropenia occurs.

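### Section 8.2 gives two restart grades after drug-related grade 3–4 toxicity, and they conflict for an event that settles at grade 2 above baseline

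*Combined protocol and SAP*

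**What the plan says.** Section 8.2 applies to both drugs and has two consecutive paragraphs on restarting.

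- The first is unqualified: "Adverse events possibly related to either study drug must be resolved to grade 1 or baseline prior to resumption of dosing".
- The second concerns grade 3–4 toxicity in patients who can be retreated: "After a two-week dose delay, if the grade 3 or 4 toxicity resolves to grades 0-2", the dose reductions of the following subsections apply. A bracketed clause requires grade 1 for one kind of grade 2 event only, peripheral neuropathy that affects instrumental ADL.

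Other text that bears on the restart decision:

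- **8.1** lists hold triggers for each drug and adds: "If treatment is delayed more than two weeks, the Principal Investigator must be contacted for further instructions on continued treatment". For interruptions beyond four weeks because of toxicity, patients "must permanently discontinue study drug unless an exemption is granted by the protocol chair".
- **8.2.1** (ascorbic acid): "One dose modification of ascorbic acid is allowed to 0.75 g/kg". It gives no recovery grade.
- **8.2.2.3** (headed as olaparib modifications): Table 8 has, for grade 3–4 cytopenias, "Dose interruption until recovered to CTCAE grade 1 or better for a maximum of 2 weeks". Table 7 requires hemoglobin of at least 10 g/dl. The parts on prolonged hematological and on non-hematological toxicity both repeat the grade 1 or baseline condition.
- **7.4** ends treatment for toxicity "that has not recovered in 2 weeks or if the same toxicity recurs at the decreased dose". It makes an exception where clinical benefit is strong enough to justify continuing, after discussion with the Principal Investigator.
- **5.2, exclusion [16]** excludes patients who "Have persistent toxicities (>Common Terminology Criteria for Adverse Event (CTCAE v5.0) grade 2) caused by previous cancer therapy, excluding alopecia". A patient can therefore enter with a grade 2 toxicity left from earlier treatment.

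**The concern.** A site that holds treatment for a drug-related grade 3 event needs one answer to one question: at what grade may dosing resume? Section 8.2 gives two. Consider a patient who had no such toxicity at baseline and is at grade 2 after two weeks. Under the first paragraph he may not be dosed. Under the second he is retreated at a reduced dose. Under 7.4 he could also be regarded as not recovered, because that section attaches no grade to recovery.

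What is at stake is dosing safety and consistent conduct. The looser rule re-doses on persisting grade 2 toxicity, in a multi-center study (section 3.0) of a combination that section 4.2.8 says has no clinical data in this disease. Two sites could each follow the protocol and handle the same patient differently.

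**Working it through.** The documents give no figure to reproduce here. The check is to apply both rules to every case and then see whether other text decides between them.

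**Step 1. The two rules.** Let *b* be the baseline grade and *s* the grade at which the event settles, each 0, 1 or 2. Exclusion [16] is why *b* = 2 is included.

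- Rule A (grade 1 or baseline): dosing may resume if *s* ≤ 1 or *s* ≤ *b*.
- Rule B (grades 0-2): dosing may resume, at a reduced dose, if *s* ≤ 2. For neuropathy affecting instrumental ADL, only if *s* ≤ 1.

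**Step 2. Toxicity other than that neuropathy (3 × 3 = 9 combinations).**

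| Settles at | Baseline | Combinations | Rule A | Rule B |
|---|---|---|---|---|
| 0 or 1 | 0, 1 or 2 | 6 | allows | allows |
| 2 | 2 | 1 | allows | allows |
| 2 | 0 or 1 | 2 | **bars** | **allows** |

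The rules disagree in 2 of 9 combinations, both at grade 2 above baseline. This counts situations and is not a probability.

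**Step 3. Neuropathy affecting instrumental ADL.** At *s* = 0 or 1 both rules allow dosing (6 combinations). At *s* = 2 with *b* = 0 or 1 both bar it (2). At *s* = 2 with *b* = 2, Rule A allows it and the clause, taken literally, bars it (1). The clause is therefore an added restriction and does not cause the conflict in step 2.

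**Step 4. Does other text decide? Olaparib.** Table 8 requires grade 1 or better. Table 7 labels hemoglobin from 8 to below 10 g/dl as grade 2, so its recovery level of 10 g/dl means better than grade 2. It has no baseline allowance, although inclusion [11] admits patients above 9 g/dL, so it can be stricter than Rule A. The remaining parts of 8.2.2.3 repeat Rule A. All of this points to grade 1 or baseline, or stricter, and grades 0-2 is the outlier.

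**Step 5. Does other text decide? Ascorbic acid.** The first paragraph of 8.2 covers it by naming either study drug, but that sentence is one side of the conflict. Sections 8.1 and 8.2.1 give hold triggers, a time limit and one dose step, and no restart grade. The non-hematological part of 8.2.2.3 speaks generically of study drug and study treatment, but under an olaparib heading and next to olaparib dose steps. It arguably reaches ascorbic acid. If it does, it repeats Rule A and leaves Rule B standing against it.

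**Step 6. Does oversight decide?** The 8.1 contact rule starts when a delay exceeds two weeks, so at exactly two weeks it is not clearly triggered. The 7.4 exception also goes through the Principal Investigator. Neither names a grade.

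**Step 7. Effect on the statistical rules.** Section 13.6 counts grade 3–4 events that have not come down to grade 2 after four weeks off drug. A patient who has settled at grade 2 by then is not counted under either restart rule. The event definition behind Table 9 and the PSA50 rule (2 or more of 12) do not depend on which rule is used.

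**The case against.** The best case against the point is that the two paragraphs can be applied together. The first sets the bar to resuming; the second then only sets the dose. On that reading grades 0-2 admits the patient who entered at grade 2, the neuropathy clause restricts him, and both paragraphs have an effect. This reading is possible, and it is the safe one. It is not the natural one. Requiring grade 1 only for a particular neuropathy implies that other grade 2 events qualify, and the second paragraph neither mentions baseline nor refers back to the first.

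The second argument is oversight. Besides 7.4 and 8.1, section 9.5.1 requires unacceptable toxicities to be reported to the Protocol Chair within 24 hours, and section 12.2 sets safety meetings weekly to monthly. In a study of 12 to 15 patients this does reduce the chance of divergent handling. It does not tell the person deciding which grade applies.

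Third, 13.6 also uses grade 2 as its line. That line defines an event for the stopping rule; it does not authorise a restart.

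Three stronger readings are tempting and are not supported:

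- A reader might infer that ascorbic acid has no restart grade anywhere. The first paragraph of 8.2 names either study drug, and the generic wording in 8.2.2.3 may also apply.
- A reader might infer that 7.4 removes the grade 2 patient automatically at two weeks. Its exception for clinical benefit, discussed with the Principal Investigator, prevents that.
- A reader might infer that every grade 2 event is in dispute. When baseline was already grade 2, both general rules allow restart.

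**Conclusion.** The conflict is real and narrow. Section 8.2 gives opposite instructions for a drug-related grade 3–4 event that settles at grade 2 in a patient whose baseline was grade 0 or 1. For olaparib, the rest of the protocol shows that grade 1 or baseline, or stricter, is meant. For ascorbic acid the text leaves more doubt, because the only further support is generic wording under an olaparib heading.

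The number of patients affected cannot be estimated: the documents give neither a grade 3–4 rate for ascorbic acid nor the share of such events that settle at grade 2. The conclusion rests on reading the second paragraph of 8.2 as a condition for retreatment, which its neuropathy clause supports. The consequence is for dosing safety and consistency between sites. Sample size, the PSA50 decision rule and the Table 9 boundaries are not affected. It should be corrected because it is a safety instruction that contradicts itself and the correction is short.

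**What to change.** In section 8.2, replace the requirement that the toxicity come down to grades 0-2 with a requirement that it come down to grade 1 or baseline. Keep the neuropathy clause as it is worded. Add a sentence stating that this restart condition applies to both olaparib and ascorbic acid, subject to the specific limits in Tables 7 and 8. Leave the 13.6 event definition unchanged.

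The drafting cost is one changed sentence and one scope statement. The clinical cost should be stated openly. Some patients with persisting grade 2 toxicity will be held longer. Those still at grade 2 above baseline after four weeks will discontinue unless the Protocol Chair grants the exemption in 8.1. They will not count as stopping-rule events under 13.6, so the safety monitoring will not register these discontinuations; they should be visible in the tabulation of reasons for stopping treatment.
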